6.2 Post-prandial Lipid Profile Analyses

6.2.1 Post-prandial Lipid Profile Analyses in Part A

Measurement of the lipids TC, TG, HDL-c, LDL-c, and non-HDL-c will be obtained just prior to the midday meal on the day of dosing and again at 0.5, 1, 2, and 4 hours post-meal for all subjects in each dosing period in Part A.

Change from baseline for each of the lipid parameters will be derived for each of the post-meal time points using the pre-meal measurement as the baseline, and the level of excursion within the 4-hour post-meal period will be determined using a post-meal area under the curve (AUC). The areas of the trapezoidal region for change from baseline between successive planned collection time points will be calculated, and these areas will be summed to obtain the AUC value.

Descriptive statistics for the post-meal AUC will be tabulated by treatment group.

An ANOVA will be conducted for each lipid parameter using post-meal AUC values. The ANOVA model will have a fixed effect for treatment and a random effect for subject. Subjects treated with Placebo for the second time during the fourth dosing period will be handled as 'new' subjects in the analysis.

Boxplots of the lipid values at pre-meal and each planned post-meal time point (0.5, 1, 2, and 4 hours post-meal) will be presented for each treatment group.

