7.3.1. Meals and Dietary Restrictions

While confined at the CRU, subjects will receive a standardized diet at scheduled times that do not conflict with other study-related activities. When not at the study site, subjects will be asked to take regular meals and avoid major deviations from their usual regimen and habits. Subjects are prohibited from consuming grapefruit or grapefruit juice during the entire duration of the study.

At required time points, subjects will be served high-fat/high-calorie lunch which must be consumed within 20-25 minutes. For subjects participating in the food effect period, a high-fat lunch will not be given. However, subjects will be required to consume a high-fat/high-calorie breakfast 30 minutes before study drug dosing. Both meals should be fully consumed by the subject.

A high-fat/high-calorie meal must contain approximately 60% fat, 20% carbohydrate, and 20% protein.

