8.2.1. Selection and Timing of Doses

Study treatment will be administered as shown in the Schedule of Events ([Appendix 2](#)).

All doses in Parts A and B should be administered in the morning under fasted conditions (12 hours), except for food effect Period 4 in Part A, which will be administered in the fed state. All doses should be administered at approximately the same time on each day for Part B (on Days 2 to 29, within ± 1 hour of dosing time of Day 1). In Part B, subjects will receive standard meals at appropriate times when confined to the CRU or during return visits for dosing. At least 60 minutes should separate the ingestion of the dose and the beginning of the breakfast meal while confined to the CRU and at home. Additionally, subjects will be asked to document time

of dosing and time of first meal in a diary and keep their standard diet when at home. A high-fat lunch meal will be administered 4 hours postdose in each period of Part A (with exception of Period 4) and on Days –1 and 28 in Part B to measure the post-prandial lipid profiles.

The actual time of all dose and initial meal administrations in the CRU will be recorded in the subject's case report form (CRF) and from the diary entries for the at-home dosings.

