- e Single 12-lead ECGs to be collected during Screening, triplicate ECGs (spaced approximately 1 minute apart) to be collected at all other time points. Subjects must be supine for at least 5 minutes prior to ECG collection. When ECG collections are scheduled at the same time point as any other tests, ECGs, followed by vital signs, must be recorded prior to any clinical laboratory, PK, PD, or biomarker blood sampling.
- f Collection to occur prior to dosing.
- g Vital signs to be measured include respiratory rate (Screening only), blood pressure, pulse rate, and temperature. Orthostatic blood pressure and pulse rate to be measured at all specified time points.
- h Refer to [Appendix 3](#) for the serum chemistry, hematology, and urinalysis clinical laboratory tests.
- i Serum pregnancy tests to be performed on female subjects only; serum FSH tests to be performed on postmenopausal female subjects only.
- j Serum TC, TG, and HDL-c will be measured; HDL-c will be used to calculate LDL-c and non-HDL-c.
- k Any leftover plasma will be stored for residual or LY3202328 metabolite assessment, after all study related needs are met.
- l Samples for serum chemistry will be obtained following a fast of at least 12 hours when a fasting lipid assessment is being performed at the same time. In case of dropouts or rechecks, subjects may not have fasted for 8 hours or 12 hours, as applicable, before the serum chemistry sample is taken.
- m Sample collection to occur just prior to meal.
- n LY3202328/placebo dosing will occur in the fasted state in all periods except the food effect period. Subjects being assessed for food effects on exposure will be given a high-fat/high-calorie meal prior to dosing during the food effect arm in Period 4.
- o A blood sample from all randomized/enrolled subjects will be collected prior to Day 1 dosing.
- p Biomarker plasma and serum collection (10 mL) should be sufficient for determination of ApoB48, lathosterol, lanosterol, desmosterol, among other biomarkers of interest.
- q Subjects will be discharged following Hour 24 procedures (i.e., Day 2).
- r A high-fat/high-calorie meal (containing approximately 60% fat, 20% carbohydrate, and 20% protein) will be given to subjects to 4 hours postdose for the post-prandial lipid assessment in all periods except for subjects in the food effect arm of Period 4.
- s Assessments can be performed any time predose

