2.1 Randomization Schedule and Unblinding Plan

Both Parts A and B are double-blinded so the subjects, investigator, and study site personnel will be blinded to treatment assignment – LY or Placebo. Simvastatin and atorvastatin dosing in Part B will also be determined by random assignment, but the subjects, investigators, and study site personnel will be unblinded to the statin assignment since commercially available product will be used. PRA Health Sciences International will be responsible for generating the schedules for both parts of the study.

In Part A, the subjects in each of the 9-patient cohorts -- Cohort 1 (1mg, 10mg, 100mg) and Cohort 2 (3mg, 30mg, 300mg) – will be randomized in a 1:1:1 ratio to one of the treatment sequences (Placebo, LY, LY), (LY, Placebo, LY), or (LY, LY, Placebo). The 30 mg dose level treatment assignments for Cohort 2 will be repeated in Period 4 to evaluate food effects on exposure. One of the period's treatment assignments for Cohort 1 will be repeated in Period 4 to evaluate the 600 mg dose level, so a couple subjects in Cohort 1 may receive Placebo twice.

In Part B, the subjects in each of four planned 10-patient cohorts -- Cohort 3 (5mg QD), Cohort 4 (20mg QD), Cohort 5 (100mg QD), and Cohort 6 (300mg QD) -- will be randomized to receive LY with simvastatin assessment (4 subjects), LY with atorvastatin assessment (4 subjects), placebo with simvastatin assessment (1 subject), or placebo with atorvastatin assessment (1 subject).

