2.2.2 Treatment Groups

During Part A, subjects will be treated in multiple dosing periods with single doses of a subset of the treatments -- Placebo, and 1mg, 3mg, 10mg, 30mg, 100mg, 300mg, or 600mg of LY. Dosing will be performed in a fasted state, except in the fourth dosing period for Cohort 2 when subjects will be dosed with 30mg LY after a standard meal. The treatment groups for Part A will be the dose levels of LY, plus the group 30mg LY fed.

During Part B, subjects will be enrolled in one of four dose-ascending groups (5mg LY, 20mg LY, 100mg LY, and 300mg LY) where they will be randomized to receive LY or placebo. The treatment groups for Part B will be Placebo, 5mg LY, 20mg LY, 100mg LY, and 300mg LY.

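### The Part A post-prandial analysis takes in the fed Period 4 of Cohort 2, which has no high-fat lunch, and pools its three placebo records with fasted placebo

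*SAP*

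**What the plan says.** SAP 6.2.1 takes lipids just before the midday meal and at 0.5, 1, 2 and 4 hours after it, "for all subjects in each dosing period in Part A". The pre-meal value is the baseline, and the trapezoidal AUC of change from it is the outcome. The ANOVA has treatment as a fixed effect and subject as a random effect. "Subjects treated with Placebo for the second time during the fourth dosing period" are entered as new subjects.

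The protocol describes a different day for the food effect period. Section 7.3.1: "For subjects participating in the food effect period, a high-fat lunch will not be given"; instead, "subjects will be required to consume a high-fat/high-calorie breakfast 30 minutes before study drug dosing". Section 8.2.1: "A high-fat lunch meal will be administered 4 hours postdose in each period of Part A (with exception of Period 4" excluded). Footnote r of the Part A Schedule of Events ties the test meal to the "post-prandial lipid assessment in all periods except for subjects in the food effect arm of Period 4".

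On who is in that period, SAP 2.1 says: "The 30 mg dose level treatment assignments for Cohort 2 will be repeated in Period 4 to evaluate food effects on exposure". On how they are grouped, SAP 2.2.2 says: "The treatment groups for Part A will be the dose levels of LY, plus the group 30mg LY fed". No fed placebo group is named.

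Two other Part A analyses leave this period out because of fed dosing: fasting lipids (SAP 6.1.1) and clinical laboratory tests (SAP 7.3.1).

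**The concern.** The endpoint is the lipid excursion after a high-fat lunch, from a baseline taken in the fasted state 4 hours after dosing. In Cohort 2 Period 4 that baseline falls about 4.5 hours after a high-fat breakfast (0.5 h before dosing plus 4 h after), and the high-fat lunch is absent. An AUC computed there under the same name is a different quantity.

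Two consequences follow. The fed placebo records enter the Placebo group, which is the reference for every fasted dose, and nothing in the model can absorb the meal difference. And the 30 mg fed group is set against placebo records of which 18 of 21 come from Periods 1–3, after a high-fat lunch, so a meal difference could be read as a drug effect. Post-prandial lipids are an exploratory objective; the primary safety conclusions are not touched.

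**Working it through.** **Inputs.** Nine subjects per cohort in three sequences, 1:1:1 (Protocol 8.2, SAP 2.1); Period 4 of Cohort 2 repeats the 30 mg assignments (SAP 2.1); the model is that of SAP 6.2.1. Not in the documents, hence assumptions: D, the fed-minus-fasted AUC difference, left as a symbol; and rho, the within-subject correlation, varied from 0 to 0.8.

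**Step 1: the plan's own allocation.** Each sequence has 3 subjects and one placebo period, so each cohort-period has 6 on LY and 3 on placebo. This reproduces the 6 and 3 per dose level in Protocol 8.2.

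**Step 2: placebo records.**
- Periods 1–3: 2 cohorts × 3 periods × 3 = 18, all fasted.
- Adding Cohort 2 Period 4: 18 + 3 = 21, of which 3 are fed; 3/21 = 14.3%.
- Adding a 600 mg Period 4 in Cohort 1 that repeats an earlier period's assignments, with the test meal given: 21 + 3 = 24; 3/24 = 12.5%.

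**Step 3: shift under the SAP model.** The generalised least squares weights were computed for this layout. With second-time placebo entered as new subjects, the placebo least squares mean shifts by 3/21 × D = 0.143 × D at every rho (3/24 × D = 0.125 × D with 600 mg). Through the random subject effect, the LY means move part of the way with it. Without the 600 mg period, each contrast of a fasted LY dose minus placebo shifts by −0.143 × (1 − rho) × D:

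| rho | size of contrast shift |
|---|---|
| 0 | 0.143 × D |
| 0.2 | 0.114 × D |
| 0.4 | 0.086 × D |
| 0.6 | 0.057 × D |
| 0.8 | 0.029 × D |

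**Step 4: the 30 mg fed group.** If the drug did nothing and the meal difference were the same on LY and placebo, the fed-minus-placebo contrast would be D − 0.143 × (1 − rho) × D. That is 0.857 × D at rho 0 and 0.971 × D at rho 0.8: nearly the whole meal difference.

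**Step 5: is the new-subject coding the cause?** The same layout was refitted with the true identifier kept and the fed records left in. The placebo mean still shifts, by 0.143 × D at rho 0 down to 0.108 × D at rho 0.8. At rho 0.4 the contrast shift is 0.071 × D for 1, 10 and 100 mg, 0.107 × D for 30 mg, and 0.196 × D for 3 and 300 mg, against 0.086 × D for all of them with new-subject coding. At rho 0.8 it is 0.234 × D for 3 and 300 mg, against 0.029 × D. The bias comes from pooling, and restoring the identifier does not remove it.

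**Step 6: after exclusion.** No fed record remains, so the shift is 0 × D. The standard error of a 300 mg minus placebo contrast, in SD units, goes from 0.463 to 0.471 at rho 0 (1.7%), from 0.388 to 0.394 at rho 0.4 (1.5%) and from 0.237 to 0.240 at rho 0.8 (1.3%).

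**The case against.** Several stronger readings are tempting, and the documents do not support them.

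- *The pooled placebo excursion is pulled down and hides triglyceride lowering at every fasted dose, while 30 mg fed shows a spurious reduction.* A smaller excursion in Period 4 is plausible, and both effects would follow from it in some degree. But no excursion data are given. The protocol withholds a high-fat lunch, which is not the same as no lunch: confined subjects receive a standardized diet, and SAP 6.2.1 speaks of a midday meal. A near-zero excursion is therefore an assumption.
- *Treatment comparisons are off by 14%.* The 14.3% is the weight of the fed records in the placebo mean. It carries over to contrasts in full only if a subject's repeated AUCs are uncorrelated.
- *Entering repeat placebo as new subjects biases the reference.* Step 5 shows otherwise; for 3, 30 and 300 mg that coding gives the smaller shift.

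Other points have some force. The group list in SAP 2.2.2 names no placebo group at all, so pooling is an inference; it is still the natural reading, since Placebo is listed there among the Part A treatments and only the 30 mg fed condition is separated. SAP section 6 says that placebo data from different periods will be reported separately. That may help the descriptive tables and boxplots, but it does not take the records out of the ANOVA. SAP 6.2.1, unlike 6.1.1, prespecifies no pairwise contrasts. Part A is not powered, and PD data are not required for dose escalation.

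The counts with 600 mg also depend on an unresolved conflict. Protocol 8.2.1 excepts all of Period 4 from the high-fat lunch; the schedule footnote excepts only the food effect arm. Under 8.2.1, Cohort 1 placebo records at Period 4 would also lack the test meal, giving 6/24 = 25% of placebo records without it.

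**Conclusion.** The point stands as an inclusion error. As written, SAP 6.2.1 computes the post-prandial AUC in a period whose meals do not produce that endpoint, and three fed placebo records join a reference group that is otherwise fasted. The shift is 0.143 × D in the placebo mean (0.125 × D if the 600 mg period is run with the test meal). In contrasts without the 600 mg period it lies between 0.143 × D and 0.029 × D in size for rho from 0 to 0.8. The 30 mg fed comparison carries most of D. These multipliers rest on the planned allocation with full retention and on the stated model. The sign and size of D cannot be had from the documents, so neither a direction of bias nor a percentage error in the drug effect can be claimed. The consequence is limited to an exploratory endpoint, but the correction is cheap and matches what the SAP already does elsewhere.

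**What to change.** Add one sentence to SAP 6.2.1 excluding Cohort 2 Period 4 from the post-meal AUC summaries, the ANOVA and the boxplots, in line with 6.1.1 and 7.3.1.

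Before deciding whether any Cohort 1 Period 4 (600 mg) records enter, reconcile Protocol 8.2.1 with footnote r of the Part A schedule on which Period 4 subjects receive the high-fat lunch, and state the answer in the SAP. If those records enter, keeping the true subject identifier for repeat placebo is a minor efficiency refinement. SAP 2.2.2 should also be reconciled with Protocol 7.3.1: the SAP calls the pre-dose meal in the fed period a standard meal, the protocol a high-fat, high-calorie one.

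Cost: SAP wording only. Nine records (6 on 30 mg fed, 3 on placebo) leave this analysis, and the standard error of the contrast checked (300 mg minus placebo) rises by about 1–2%. The fed-versus-fasted exposure comparison uses PK data and is unaffected.

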6.1 Fasting Lipid Profile Analyses

6.1.1 Fasting Lipid Profile Analyses in Part A

A fasting lipid profile will be collected from all subjects in each dosing period in Part A, except for dosing period 4 for Cohort 2 which prescribes dosing subjects in a fed state. Fasting measurements of TG, TC, and HDL-c will be obtained and fasting measurements of LDL-c and non-HDL-c will be derived from plasma samples collected just prior to dosing on the day of dosing, then at 24, 48 and 96 hours after dosing.

A last observation measurement will be derived for each subject using the last post-dose measurement of a lipid parameter. Change from baseline for each of the lipid parameters will be derived for each of the post-dosing time points (Day 1 [24 hours], Day 2 [48 hours], and Day 4 [96 hours]) and the last observation using the pre-dose measurement from the day of dosing as the baseline.

Descriptive statistics for the measurement at baseline and the measurement and change from baseline at each post-dose time point plus the last observation will be tabulated.

A mixed-effect repeated measures (MMRM) analyses will be conducted for each lipid parameter using the change from baseline values from Days 1, 2, and 4. The MMRM model for change from baseline will contain fixed effects for treatment, time, and their interaction, a random effect for subject, and the baseline measurement as a covariate. The covariance structure among the repeated measurements for a subject will be assumed to be common across subjects and modeled using an unstructured 3x3 matrix. Satterthwaite's approximation will be used to estimate denominator degrees of freedom. Any missing assessments will be assumed to be missing at random, so estimates of treatment effects from the model will be assumed to be unbiased. These analyses will be performed using the SAS procedure PROC MIXED. The tabular output for these MMRM analyses will present the least squares means, standard errors and 95% confidence intervals and Type 3 p-values for each main effect marginal. Pairwise contrasts of the least squares means between the LY dose levels and placebo along with the associated 95% confidence interval and Type 3 p-values will also be provided at each time point using LSMESTIMATE statements.

Plots of the least squares mean \pm standard error estimates for each lipid parameter over time (pre-dose through Day 4 post-dose) will be provided by treatment group.

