6.2.2 Post-prandial Lipid Profile Analyses in Part B

Measurement of the lipids TC, TG, HDL-c, LDL-c, and non-HDL-c will be obtained just prior to the midday meal on Days -1 and 28 of dosing. Post-meal measurements will be collected on both days at 0.5, 1, 2, and 4 hours after the meal for all subjects in Part B.

Change from baseline for each of the lipid parameters will be derived for each of the post-meal time points using the pre-meal measurement as the baseline, and the level of excursion within the 4-hour post-meal period will be determined using the post-meal AUC, as described in Section 6.2.1.

Descriptive statistics for the post-meal AUC at Days -1 and 28 as well as the difference between Days -1 and 28 will be presented by treatment group.

An ANCOVA will be conducted for each lipid parameter using the difference in post-meal AUC values from Day -1 to Day 28. The ANCOVA model will have a fixed effect for treatment, a random effect for subject, and the Day -1 post-meal AUC as a covariate.

Boxplots of the lipid values at pre-meal and each planned post-meal time point (0.5, 1, 2, and 4 hours post-meal) will be presented for each treatment group for both Day -1 and Day 28.

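### The Part A post-prandial lipid ANOVA (SAP 6.2.1) has no pre-treatment covariate, although a pre-dose fasting value is drawn in every fasted period; it may be less precise than the data allow

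*SAP*

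**What the plan says.** SAP 6.2.1 measures TC, TG, HDL-c, LDL-c and non-HDL-c just before the midday meal and at 0.5, 1, 2 and 4 hours after it. The outcome is an AUC of change from the pre-meal value: "The areas of the trapezoidal region for change from baseline between successive planned collection time points will be calculated", and the areas are then summed. On the model it says: "The ANOVA model will have a fixed effect for treatment and a random effect for subject". No covariate is named, and the section lists no pairwise contrasts or confidence intervals.

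The neighbouring models all adjust:

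- **SAP 6.1.1 (Part A fasting lipids, same subjects).** Both the repeated-measures model and the last-observation ANCOVA use baseline. The first has "a random effect for subject, and the baseline measurement as a covariate". That baseline is the pre-dose value of the same period; the fasting lipids are "derived from plasma samples collected just prior to dosing on the day of dosing, then at 24, 48 and 96 hours after dosing".
- **SAP 6.1.2 and 6.3 (Part B fasting lipids and biomarkers).** Every model has the baseline value as a covariate.
- **SAP 6.2.2 (Part B post-prandial).** The ANCOVA has "a random effect for subject, and the Day -1 post-meal AUC as a covariate".

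There is one exception to the availability of the pre-dose fasting value. SAP 6.1.1 takes the fasting profile in each Part A period "except for dosing period 4 for Cohort 2 which prescribes dosing subjects in a fed state".

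**The concern.** The SAP gives no reason why 6.2.1 alone has no pre-treatment covariate. The pre-meal value subtracted inside the AUC cannot serve as one. Protocol 8.2.1 puts the high-fat lunch 4 hours after the dose, so the pre-meal sample may already reflect treatment. The random subject effect removes stable differences between subjects, but not shifts in a subject's fasting lipids from one period to the next. The pre-dose sample measures those shifts.

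What is at stake is precision. Each Part A dose has 6 subjects on LY3202328. Residual variance that a collected value could explain would widen the intervals, and chance differences between periods in fasting lipids would stay in the treatment estimates.

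**Working it through.** The plan states no power, effect size, SD or correlation for this analysis, so there is no planned figure to reproduce. The check is what the covariate could gain or cost in the planned layout.

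**Inputs from the documents.** Part A has two cohorts of 9, each randomised 1:1:1 to three sequences (Protocol 8.2, SAP 2.1), and each subject receives two active doses and one placebo. For Periods 1 to 3:

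- subjects: 18
- subject-periods: 18 × 3 = 54
- records: 18 on placebo and 6 on each of six doses
- within-subject degrees of freedom: 54 − 18 − 6 = 30

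**Assumed, because the documents are silent.** Rho is the within-subject, period-to-period correlation between the pre-dose lipid and the incremental post-meal AUC, taken from 0 to 0.7. The between-subject share of AUC variance is taken as 0.5 or 0.7.

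**What the subject effect already does.** In total-SD units, with no between-subject variance, the standard error of dose minus placebo is √(1/6 + 1/18) = 0.471. With the planned random subject effect it is 0.365 if the between-subject share is 0.5, and 0.290 if it is 0.7. That gain needs no covariate.

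**What the covariate adds.** The covariate multiplies residual variance by (1 − rho²), and estimating its slope inflates the variance by (df − 1)/(df − 2) = 29/28. So

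SE ratio (with ÷ without covariate) = √[(1 − rho²) × 29/28].

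The ratio is 1 when rho² = 1/29, that is rho = 0.19.

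The simulated column refits the SAP model by REML, with and without the covariate, 700 runs per setting. It gives the range over both between-subject shares and between-subject correlations of 0 and 0.5. The power column uses the non-central t, two-sided 5%, starting from 60% power on 30 df and using 29 df with the covariate.

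| rho | SE ratio, formula | SE ratio, simulated | Power change from 60% (points) |
|---|---|---|---|
| 0 | 1.018 | 1.01–1.02 | −1.6 |
| 0.1 | 1.013 | 1.00–1.01 | −1.2 |
| 0.2 | 0.997 | 0.99–1.00 | +0.1 |
| 0.3 | 0.971 | 0.96–0.98 | +2.4 |
| 0.4 | 0.933 | not run | +5.9 |
| 0.5 | 0.881 | 0.87–0.90 | +10.8 |
| 0.7 | 0.727 | 0.74–0.75 | not run |

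A 5-point gain needs rho of 0.39, 0.38 and 0.40 from base powers of 50%, 60% and 80%, so about 0.4. The slope-estimation factor matters at this size: without it the gains at rho 0.2 and 0.3 would read 1.7 and 4.0 points.

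**The case against.** The strongest defence is that nothing equivalent was left out. The other models adjust for a baseline of the variable they analyse; in 6.2.2 that is a Day -1 post-meal AUC. Part A has no pre-treatment post-meal AUC. The candidate here is a fasting level, set against an excursion already net of the pre-meal value, and the two need not correlate. Part B is also parallel-group, whereas Part A subjects act as their own controls and the subject effect already does most of the work. All of this stands, and it is why the gain is conditional.

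It does not remove the point. The closest comparator is SAP 6.1.1, which covers the same crossover with the same random subject effect and still adjusts for the period's pre-dose value. So the SAP does not treat the subject effect as a substitute for a period-specific baseline. Subtracting a baseline is no substitute either: the SAP's fasting models subtract it and adjust for it as well.

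A reader might also infer three stronger things, none of which the documents support:

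- **That the pre-dose fasting value exists in every period.** SAP 6.1.1 excludes Cohort 2 Period 4.
- **That the omission breaks the protocol's PD default.** The ANCOVA default in Protocol 11.3.3 is worded for endpoints with only baseline and end-of-therapy measurements, and further covariates are optional. The planned ANOVA is a valid crossover analysis.
- **That the search for a dose showing target engagement is affected.** Protocol 10.6 frames that search as a comparison of Day -1 with Day 28, which is Part B.

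**Conclusion.** The point holds as a minor one. SAP 6.2.1 is the only model of its kind without a pre-treatment covariate, no reason is given, and a suitable value is already collected in the fasted periods. It is tempting to conclude that the Part A comparisons are less precise than they could be. The documents support only that they may be, because rho is not given for any of the five lipids and may differ between them.

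Under the assumptions above, the effect on the standard error runs from about 2% worse at rho 0 to about 12% better at rho 0.5, with break-even near 0.19. The trade is asymmetric in favour of the covariate. The power figures are only a yardstick, since 6.2.1 names no dose contrasts, post-prandial lipids are an exploratory objective, and Protocol 11.1 says Part A is not powered for hypothesis testing.

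**What to change.** For the fasted periods, pre-specify the 6.2.1 model as a fixed effect for treatment, a random effect for subject, and that period's Day 1 hour 0 pre-dose fasting value of the same lipid as a covariate. State that the 4-hour pre-meal value is not to be used as the covariate, because it is post-dose.

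Summarise the Cohort 2 Period 4 fed records separately, since no fasting profile is taken there and they would otherwise drop out of the model. In the same edit, reconcile SAP 6.2.1, which describes post-meal sampling in each Part A period, with Protocol 8.2.1, which gives no high-fat lunch in Period 4.

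The cost is a short SAP edit, one degree of freedom, and intervals up to about 2% wider if the correlation is near zero. No new sample is needed: the Part A schedule (Protocol Appendix 2) already has the lipid draw at hour 0, before dosing. If the sponsor prefers the unadjusted model, one sentence giving the reason would settle the point.
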